University of Kansas Medical Center
RESEARCH PROTOCOL INVOLVING HUMAN SUBJECTS TEMPLATE

Version date: October 1, 2018

Principal Investigator: [name], MS

Study Title: An open-label pilot study of the effect of intra-articular bilateral knee injections of Zilretta on OARSI recommended physical performance measures in adults with symptomatic knee osteoarthritis.

Co-Investigator(s): [name]

I. Purpose, Background, and Rationale

A. Aim and Hypotheses

This study will be an open-label trial to determine the functional effects of bilateral IA injections of Zilretta into knee joints of 70 subjects with bilateral KL grade 2-4 symptomatic knee osteoarthritis (OA). Measurement and evaluation of outcomes at baseline, 6, 12 and 24 weeks will allow assessment of short and long-term effects, consistent with Osteoarthritis Research Society International (OARSI) and Outcome Measures in Rheumatology (OMERACT) recommendations.

The **primary** aim of the proposed study is to demonstrate the effect of IA injection of Zilretta on physical performance measures in adults with bilateral knee OA. We will test this primary study endpoint by assessing the change in OARSI recommended physical performance tests¹ (30-second chair standing test, 40m fast-paced walking test, stair ascent) 6, 12 (primary) and 24 weeks after treatment.

The secondary outcome will be the change in Knee Injury and Osteoarthritis Outcome Score (KOOS-PS) at 6, 12 (main) and 24 weeks after treatment. This will be captured using the patient-reported physical function short form.

The tertiary outcomes will be the change in KOOS-Quality of life subscale (QoL) and Numerical Rating Scale (NRS) for pain. While the primary outcomes will be defined at the 12-week follow-up, all outcomes will be assessed at the 6- and 24-week follow-up as well to define the course and trajectory of effects.

We hypothesize that people with bilateral symptomatic knee OA will experience significant improvement in physical performance, physical function and quality of life for at least 12 weeks following treatment. Based on research done using Zilretta in patients with knee OA, we anticipate that it will have a greater magnitude and duration of analgesic effect along with significantly fewer adverse events when compared to the rates reported for standard of care therapy (i.e. immediate release corticosteroid injection).²

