This will be an open-label study to determine the functional effects of IA injection of Zilretta into bilateral knees of 70 subjects with KL grade 2-4 symptomatic knee OA. Measurement of OARSI recommended physical performance measures¹⁰, patient-reported physical function, quality of life and pain at baseline, 6, 12 and 24 weeks will allow assessment of short and long-term effects, consistent with OARSI and OMERACT recommendations. Adverse events will be monitored.

Each subject will participate for up to 24 weeks following the intra-articular Zilretta injection. Enrollment is expected to take approximately 6 months. Total study duration is expected to require at least 12 months.

C. Sample size, statistical methods, and power calculation

In this open-label study, all subjects will receive a single IA Zilretta injection into each knee. Outcome measures will be collected at baseline, 6, 12 (primary) and 24 weeks post-treatment. A 24-week follow-up duration was selected to detect meaningful differences from standard of care (IA corticosteroids - TAcS) and long-term effects, while minimizing the variability that may occur further out from treatment. The overall type I error rate will be controlled with an alpha level of 0.0167 to account for three comparisons at the primary time point.

Based on the respective MDC₉₅ calculated from the standard error of the mean change for OARSI recommended physical performance¹, the effect size for this minimal detectable change is 0.392. To detect an effect size at least this large, with an adjusted alpha of 0.0167 and 80% power, a sample size of 60 would be required. To accommodate up to 14% dropout, we plan to recruit 70 subjects.

D. Subject Criteria (See Vulnerable Populations appendix, if applicable):

Enrollment will be comprised of 70 subjects age 30 and over with symptomatic bilateral knee OA. There will be no exclusions based on sex or ethnic group. Potential subjects will be identified through hospital records, referrals from physicians in the surrounding community, mass mailings, and advertisements posted in area clinics and businesses. Any study-related advertisements will be approved by the IRB prior to use. Subjects will be recruited based upon inclusion and exclusion criteria detailed below.

1. Inclusion Criteria

- Men and women age 30 years or older with symptomatic bilateral knee OA.

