- Symptomatic Knee OA will be defined as the presence of a definite osteophyte or joint space narrowing (KL Grade ≥ 2) on posteroanterior (PA) fixed flexion knee radiographs in subjects limited by bilateral pain in each knee, rated on a Numerical Rating Scale as $\geq 4/10$ on more than half of the days over the past month. Radiographic change must be visible at standard image size, irrespective of capability to detect more subtle changes through digital enhancement.
- Bilateral knee symptoms for ≥ 3 months prior to screening.
- Undergone at least one prior conservative osteoarthritis treatment (e.g. physical therapy, analgesics).
- Body Mass Index ≤ 40 kg/m².
- Ambulatory.
- Willing and able to comply with the study procedures and visit schedules and ability to follow verbal and written instructions.
- Willing to abstain from the use of protocol-restricted medications during the study after signing Informed Consent (Refer to §II.5) and also willing to abstain from use of all analgesics other than acetaminophen 1 week prior to the beginning of treatment.

2. Exclusion Criteria

- Current consumption of more than 14 alcoholic drinks per week.
- Clinical signs and symptoms of active knee infection or crystal disease of either knee within 1 month of screening.
- Diagnosed with rheumatoid arthritis, Reiter's syndrome, psoriatic arthritis, gout, ankylosing spondylitis, or arthritis secondary to other inflammatory diseases; HIV, viral hepatitis; chondrocalcinosis, Paget's disease, or villonodular synovitis.
- Diagnosed with leukemia, known presence of metastatic malignant cells, or ongoing or planned chemotherapeutic treatment.
- Diseases of the spine, hip or other lower extremity joints judged by the investigator to be contributing to the pain in either knee (i.e. sciatica, nerve pain, hip OA). Note: Patients with hip replacement in either hip may be enrolled provided there is sufficient pain relief after hip replacement that analgesics are not required
- Untreated symptomatic injury of either knee (e.g., acute traumatic injury, anterior cruciate ligament injury, clinically symptomatic meniscus injury characterized by a mechanical issue such as locking or catching).
- Uncontrolled diabetes.

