- Women who report pregnancy or childbearing potential and not using acceptable contraceptive measures (oral contraceptive, long acting reversible contraceptive therapy) (due to the potential for change in body mass and distribution to alter knee symptoms over the period of follow-up).
- Presence of surgical hardware or other foreign body intended to treat arthritis or cartilage-related pathology in either knee.
- Arthroscopy or open surgery of either knee within 6 months of screening.
- Planned/anticipated surgery of either knee during the study period.
- Use of systemic immunosuppressant within 6 weeks of screening.
- Oral corticosteroids (investigational or marketed) within 2 weeks of screening.
- IA corticosteroid (investigational or marketed) in either knee within 3 months of screening.
- IV or IM corticosteroid (investigational or marketed) within 3 months of screening.
- Any other IA drug/biologic use within 6 months of screening or 5 half-lives (whichever is longer) (e.g., hyaluronic acid, platelet-rich plasma (PRP) injection, stem cells, prolotherapy and amniotic fluid injection).
- Any documented clinically significant degree of cognitive impairment or other condition, finding, or psychiatric illness at screening which, in the opinion of the investigator, could compromise subject safety.
- Any condition other than OA of the knee which, in the opinion of the investigator, affects the ability to ambulate to a sufficient degree to interfere with the assessment of the safety and treatment effects of the study injection.
- Participated in any investigational drug or device trial within 30 days prior to screening or concurrent participation in another research study that could complicate interpretation of the study findings.

3. Withdrawal/Termination criteria:

Subjects may discontinue the study at any time. The investigator may discontinue a subject at any time for subject safety or noncompliance. Subjects who are discontinued for safety will be referred to their primary care physician for follow-up.

The Investigator/Coordinator will complete a study exit form in the CRF for any subject who prematurely discontinues from the study. If discontinuation was the result of an AE, the AE also will be recorded in the CRF.

4. Allowable Medications/Nonpharmacological Therapies

The following medications and nonpharmacological therapies may be taken or used throughout the study:

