- Aspirin for cardio-protection at a maximum stable dose provided the dose was stabilized over 3 months prior to study entry.
- Physical therapy/bracing for the knee joint if the program was initiated and consistent prior to study entry.
- Acetaminophen may be taken (up to 3000 mg per day) as rescue medication, if needed. Rescue medication is used only to treat worsening pain, whether or not that pain is associated with knee (e.g, may be used to treat headache, acute injury, etc.) and is not used for prophylaxis.
- Use of acetaminophen must be discontinued 48 hours prior to the procedure visit and each follow-up visit.

5. Restricted Medications/Nonpharmacological Therapies

Volunteers will be advised that participation in the study will require them to abstain from certain medications and therapies. The following medications and nonpharmacological therapies should not be taken or used beginning immediately upon enrollment (after signing informed consent) until subject reaches the end of the study:

- Oral non-steroidal anti-inflammatory drugs (unless on a chronic stable dose for ≥ 3 months prior to enrollment).
- Topical analgesics applied to the skin over the knee (e.g., NSAID's, capsaicin, lidocaine, heat patches).
- Orally administered systemic corticosteroids.
- Other Intra-articular injection into the knee joint.
- Centrally acting pain medications (e.g., pregabalin, gabapentin, duloxetine, milnacipran) (unless on a chronic stable dose for ≥ 3 months prior to enrollment).

E. Specific methods and techniques used throughout the study

Investigational Product

Zilretta kits will be received from Flexion Therapeutics and stored in a refrigerator between 2-8 degrees Celsius upon receipt. An 'Investigational Drug Accountability Record' will be used to record the product use for each subject. The kit label number, date of receipt, dates of dispense and preparation, and the date of destruction of the remaining product will be tracked and logged.

Treatment Procedure:

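### Discontinuing a subject for undefined noncompliance after a one-time injection can only end outcome collection, and may remove poor responders from the week-12 test

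*Combined protocol and SAP*

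**What the plan says.** Four parts of the protocol bear on this point.

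- **Discontinuation (II.D.3).** "The investigator may discontinue a subject at any time for subject safety or noncompliance". Noncompliance is not defined. What follows is administrative: "The Investigator/Coordinator will complete a study exit form in the CRF for any subject who prematurely discontinues from the study". Subjects discontinued for safety are also referred to their own physician. The available text describes no outcome visit after discontinuation.
- **Treatment (II.C).** "all subjects will receive a single IA Zilretta injection into each knee". The schedule table places it at Visit 2, Day 1.
- **Duties that remain after Day 1.** Section II.D.5 lists therapies that "should not be taken or used beginning immediately upon enrollment (after signing informed consent) until subject reaches the end of the study". They are oral NSAIDs and centrally acting pain drugs (both excepted on a chronic stable dose), topical analgesics over the knee, oral corticosteroids, and other knee injections. Section II.D.4 adds: "Use of acetaminophen must be discontinued 48 hours prior to the procedure visit and each follow-up visit". The inclusion criteria also require subjects to be "Willing and able to comply with the study procedures and visit schedules and ability to follow verbal and written instructions".
- **Analysis (V.A).** The primary analysis is a one-sample t-test on each of three baseline-to-week-12 change scores at 0.05/3. Other time points, and the secondary and tertiary outcomes, go to repeated-measures analysis, described as longitudinal mixed models. The available text names no analysis population, missing-data method or sensitivity analysis.

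**The concern.** When treatment is repeated, discontinuing a noncompliant subject may at least stop the treatment. Here treatment is complete on Day 1, so the rule can only stop measurement. Much of what a subject can still fail to comply with is abstention from other pain treatment. A subject whose knee pain has returned has more reason to break that duty than one who is doing well. The decision rests with an investigator who, in an open-label trial, can see how the subject is doing.

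The primary test uses only subjects with both a baseline and a week-12 value. If those removed tend to be poor responders, the mean change among those left is too high, and a single-arm trial has no control group to reveal or offset this. Section I.A also says that "all outcomes will be assessed at the 6- and 24-week follow-up as well to define the course and trajectory of effects", and a trajectory estimated on a selectively reduced group can mislead. A value that was never collected cannot be recovered by analysis.

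**Working it through.** **1. Inputs.** From II.C: effect size 0.392 (taken as SD units of change), alpha 0.0167, power 80%, 60 evaluable subjects, up to 14% dropout, 70 recruited. From V.A: one-sample t-test on change. The documents give no rate of discontinuation for noncompliance and no relation between discontinuation and response, so both are assumed below.

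**2. The plan's own figures.** With the noncentral t distribution, d = 0.392 and one-sided alpha 0.0167, the smallest n with at least 80% power is 60 (power 80.3%). Inflation gives 60/(1 − 0.14) = 69.8, so 70. Both figures reproduce. (A two-sided test would need 71, and the plan does not state sidedness. That is a separate matter.)

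**3. Selection model for the week-12 t-test.** Let Y be the standardised week-12 change, with improvement positive. A subject is lost when a latent normal score, correlated ρ with Y, falls below the cut-off c = Φ⁻¹(d), where d is the proportion lost. The bias in the completers' mean is then

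bias = ρ × φ(c)/(1 − d).

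For d = 0.14, c = −1.080, φ(c) = 0.2226, and φ(c)/(1 − d) = 0.2226/0.86 = 0.259. For 70 enrolled and a true change of zero, a simulation of 40,000 trials gave the false-positive rates in the last column.

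| ρ | Bias (SD) | As % of 0.392 | Simulated one-sided error rate (nominal 0.0167) |
|---|---|---|---|
| 0 | 0 | 0% | 0.018 |
| 0.2 | +0.052 | 13% | 0.041 |
| 0.3 | +0.078 | 20% | 0.063 |
| 0.5 | +0.129 | 33% | 0.132 |
| 1 (exactly the worst 14% lost) | +0.259 | 66% | 0.626 |

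The row ρ = 1 is an upper bound, not a forecast. Over the same span of ρ, the bias runs from 0 to +0.109 at 5% loss and from 0 to +0.350 at 20% loss.

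**4. What a likelihood-based model can recover.** Suppose loss after week 6 depends only on the observed week-6 value (the lowest 14% are lost), with a within-subject correlation between visits of 0.3, 0.5 or 0.7. The completers' mean at the next visit is biased by +0.08, +0.13 or +0.18 SD. An estimate that also uses the week-6 value is within 0.003 of the truth in all three cases. A mixed model therefore tolerates loss that earlier visits explain. It does not correct loss prompted by worsening between visits, and follow-up visits are 6 and then 12 weeks apart.

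**The case against.** The strongest reply is that the protocol nowhere directs the removal of subjects whose benefit fades. The rule is permissive. Section II.D.5 attaches no consequence to using a restricted therapy. Noncompliance can equally mean missed visits, missed procedures or a missed acetaminophen washout, none of which need be related to response. Subjects whose pain returns also have permitted options: acetaminophen as rescue, an established physical therapy or bracing programme, and NSAIDs or centrally acting drugs already taken on a chronic stable dose. All of this stands, and it is why the bias range starts at zero.

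The size can also be small. With a true mean of 0.392 and three of 70 subjects removed, each with zero change, the completers' mean is (70 × 0.392)/67 = 27.44/67 = 0.410, an excess of 0.018 SD. The 14% allowance must cover every cause of loss, not this one alone, and removals after week 12 cannot affect the primary endpoint.

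A reader might infer that the rule inflates durability at week 12 and week 24 alike. The documents do not support that. A completers' mean is not the planned week-24 analysis, and step 4 of the working shows that the mixed model is exposed only to loss driven by unobserved worsening.

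Finally, keeping these subjects does not by itself guarantee an unbiased result. Values measured after another analgesic or injection may also look better, and with one arm that improvement would be credited to the study drug. This stands and shapes the remedy. It argues for stating how such values are used, not for leaving them uncollected.

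Some safeguards exist already: concomitant medications are reviewed at every visit, and premature terminations are reported monthly. Neither yields an outcome value after discontinuation. Part of the protocol was not available, so the absence of further follow-up is a statement about the available text only.

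**Conclusion.** The point holds as a risk, not as a demonstrated bias. Because treatment is a single Day 1 injection per knee, discontinuation for noncompliance can only end measurement. Some foreseeable noncompliance is related to poor response, and the primary week-12 test omits anyone without a week-12 value.

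The size is unknown. At the planned 14% loss the bias in the week-12 completers' mean is 0 if loss is unrelated to response, about +0.05 to +0.13 SD at correlations of 0.2 to 0.5, and +0.26 SD at the upper bound, against a design effect of 0.392. These figures assume normal change scores, a threshold model for loss, and the whole dropout allowance lost before week 12. The concern is weaker at week 24, for the reason given under the objection. The change is worth making because it is cheap and cannot be made after the data have been missed.

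**What to change.** 1. In II.D.3, state that noncompliance, including use of a restricted therapy, does not end outcome collection. Injected subjects are asked to attend the 6-, 12- and 24-week assessments (performance tests, KOOS-PS, KOOS-QoL, pain NRS) unless they withdraw consent or are discontinued for safety.
2. At the concomitant-medication reviews already scheduled at each visit, record the date and type of any restricted therapy.
3. In V.A, prespecify how values obtained after restricted therapy enter the analysis. Report results both with those values as observed and with those visits scored as no improvement.

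The cost is a short addition to each of II.D.3 and V.A, and one further analysis. The visits are already scheduled. The downside is that some retained values are measured on other therapies and could look better for that reason, so both analyses must be shown. This concerns data collection and analysis only and changes no clinical care.

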Zilretta (triamcinolone acetonide extended-release injectable suspension) is indicated as an intra-articular injection for the management of pain due to knee OA. To prepare the injectate, we will dilute 32 mg Zilretta in a 5 ml diluent for each knee, per manufacturer instructions. After application of sterile chlorhexidine and topical lidocaine (optional) for skin anesthesia, we will locate the superior recess of each knee joint, aspirate excess joint fluid and then inject the 5ml injectate into each knee joint capsule (bilateral injections).

Primary Outcome

OARSI recommended physical performance measures

OARSI (Osteoarthritis Research Society International) recommended physical performance measures¹ are a consensus-derived set that test physical function, which is complementary to patient-reported measures for

use in people diagnosed with knee osteoarthritis or following knee replacement. They are recommended for use prospectively as outcome measures in research, and also in clinical practice to make treatment decisions based on the results¹¹.

1. 30-second chair standing test

The 30-second chair standing test evaluates the maximum number of repetitions that a subject can stand from a seated position in a 30 second period¹. From the sitting position, the subject will stand up completely up so hips and knees are fully extended, then completely back in the seated position. This will be repeated for 30 seconds and we will record the total number of chair stands (up and down equals one stand). The tester will stand close to the side of the chair for safety and also ensure that the subject comes to a full standing and sitting position during the test.

The study coordinator or designee will enter the data collected into the CRF after completion of the test.

2. 40m fast-paced walking test

The 40-meter fast-paced walking test is a test that is timed over 4 x 10m (33 ft) paths for a total of 40 m (132 ft)¹. We will mark out a 10 m (33 ft) walkway with bright colored tape at each end. A cone will be placed approximately 2 meters before the start mark and 2 meters beyond the finish mark of the 10m walkway. Enough space will be left to turn safely around at each end.

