A practice trial of 1-2 turns will be done before testing to help subjects to understand the procedure. We will begin timing subjects after giving the signal to start at the start line and stop the timer once the subject crosses back over the start line after completing the course. When the subject crosses the 10m mark, timing will be paused while the subject turns around the cone and then it will be resumed once they cross the 10m mark again. The same will be repeated for the following turns and timing will be stopped once the subject crosses the start line for the final time. The duration of one trial will be recorded to the nearest 100th of a second. Time of one test trial will be recorded and expressed as speed (m/s) by dividing distance (40m) by total time. Regular walking aid will be allowed and its use will be recorded.

For subjects in whom safety is of concern, the tester will follow slightly behind and off to one side of the subject, while taking care not to pace or impede them. If there is no excess concern for safety, the tester will follow well to the side so as to view the crossing at the 10m walkway at both ends. The study coordinator or designee will enter the data into the CRF.

3. Stair negotiation

Stair negotiation is also a common activity limitation and rehabilitation goal in people with symptomatic knee OA. We will time the subjects ascending and descending a flight of 9 stairs as quickly as they can accomplish in a safe manner. We will conduct the nine-step stair test in the staircase adjoining our research space (individual step height of 17 cm).

Timing will begin on the signal to start and terminate when the subject returns with both feet to the ground level. Total time to ascend and descend steps for 1 test trial will be recorded to the nearest 100th of a second.

Use of a handrail and walking aid will be permitted if required¹. The study coordinator or designee will enter the data into the CRF.

Secondary Outcome

Patient-reported physical function (KOOS-PS).

In addition to the performance-based primary outcome measures, KOOS-PS, a self-reported measure of mobility will be included.

KOOS-Physical Function (KOOS-PS) Short Form is a parsimonious measure of physical function derived from the KOOS¹². The KOOS-Physical Function Short Form also has good internal consistency and high

test-retest reliability.

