Data regarding subject's demographic, knee radiographs, OARSI recommended physical performance measures, and KOOS subscale responses and NRS pain data will be obtained directly from subjects. All data will be coded with no information that could identify a subject. A master list with patient information and assigned study ID's will be stored in a password-protected file available only to the Principal Investigator and the Research Coordinator. Analyses will be performed on coded files. Physical files (e.g. questionnaires) will be stored in locked file cabinets in the office of the Principal Investigator.

E. Quality Assurance / Monitoring

Study staff will have proper qualifications for data entry and will receive training in data entry procedures to ensure data entered is of highest quality. Data will be entered by researchers into two separate databases developed for this study. Each database will contain the same collection points and then be reconciled to clean the data for analysis and outcome reports to the Principal Investigator. Data will be backed-up daily.

V. Data Analysis and Reporting

A. Statistical and Data Analysis:

The primary analysis will regard the change in the 3 OARSI-recommended physical performance measures between baseline and 12 weeks following injections. The three pre/post change scores will be assessed with one-sample t-test for matched pairs, using an alpha level of (.05/3) to determine statistical significant change.

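### Practice is described only for the walk test; brief practice before the chair-stand and stair tests would cheaply reduce any learning effect, which this single-arm comparison cannot separate from treatment

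*Combined protocol and SAP*

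**What the plan says.** Section II.E describes the three performance tests that make up the primary outcome.

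- **40 m walk:** "A practice trial of 1-2 turns will be done before testing to help subjects to understand the procedure". One trial is then recorded.
- **30-second chair stand:** "This will be repeated for 30 seconds and we will record the total number of chair stands". No practice is described, and the number of trials is not stated.
- **Stairs:** "Total time to ascend and descend steps for 1 test trial will be recorded to the nearest 100th of a second". No practice is described.

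Section II.C sets the design: "In this open-label study, all subjects will receive a single IA Zilretta injection into each knee". There is no untreated or placebo group. Section V.A sets the primary analysis of change from baseline to 12 weeks: "The three pre/post change scores will be assessed with one-sample t-test for matched pairs", "using an alpha level of (.05/3) to determine statistical significant change". Nowhere does the document describe a familiarisation session, a repeated baseline or an analysis adjustment for learning.

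**The concern.** The protocol gives its own reason for the walk-test practice, which is that subjects should understand what is asked of them. It does not say why that reason stops at one of three primary measures.

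On the other two tests the baseline score may be a first attempt. By week 12 the subject has done the test at baseline and again at week 6. If unfamiliarity holds back a first attempt and the familiarity lasts, later scores improve without any drug effect, with more stands and a shorter stair time. That is the direction of the study hypothesis. A control arm would show the same learning and allow it to be subtracted. A test of change against zero has nothing to subtract, so a learning gain would be credited to the injection.

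**Working it through.** **Inputs**

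- Three tests, each at alpha .05/3 = 0.0167 (II.C, V.A).
- Analysis: "one-sample t-test for matched pairs" (V.A). Whether it is one- or two-sided is not stated, so both are shown.
- Design effect size 0.392, 80% power, 60 subjects needed, 70 recruited to allow for 14% dropout (II.C).
- Baseline performance is taken as measured, as the text in I.A, II.B and IV.A requires. The row for these tests in the schedule table, as extracted, shows marks only at the follow-up visits, but the table may be broken.
- Size of learning: not in the documents. It is an assumption, L, in units of the SD of the change score.

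**The plan's own figure.** For a paired t-test, power comes from the noncentral t distribution with n − 1 degrees of freedom and noncentrality d√n. With d = 0.392 and n = 60, the noncentrality is 0.392 × 7.746 = 3.04. One-sided at 0.0167, power is 80.2%, so 60 reproduces. Two-sided, power at 60 is 71.5%. Dropout: 60 / 0.86 = 69.8, rounded up to 70, which matches.

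**How learning enters.** In a single-arm test against zero,

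expected change = drug effect + learning + other non-drug change.

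Learning therefore adds one-for-one to the estimate. With no drug effect and no other change, the noncentrality is L√60. The critical value on 59 degrees of freedom is 2.464 two-sided and 2.179 one-sided. The chance of significance is the probability that this noncentral t exceeds the critical value. The two-sided figure also includes the opposite tail, which is negligible from L = 0.1 upwards.

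| Assumed L (SD of change) | L√60 | Two-sided | One-sided |
|---|---|---|---|
| 0 | 0 | 1.7% | 1.7% |
| 0.05 | 0.39 | 2.5% | 4.0% |
| 0.10 | 0.77 | 5.2% | 8.6% |
| 0.20 | 1.55 | 18.9% | 27.1% |
| 0.30 | 2.32 | 45.0% | 56.0% |

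These are chances per affected test. They show how sensitive the analysis is to learning and do not estimate how much learning there is.

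**The case against.** **The size is assumed.** Nothing in the documents says that learning occurs on the chair-stand or stair test, or how large it is. At 0.05 SD the two-sided rate rises only from 1.7% to 2.5%. Learning would also have to last across the weeks between visits. This stands. A reader might infer that two of the three primary outcomes are inflated. The documents support only that learning, if present, could not be separated from treatment.

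**The difference between tests may be deliberate.** The walk test has a marked course, cones, several turns and paused timing, whereas standing up and climbing stairs are everyday acts. This is a fair reason to expect less learning on those two tests. It does not exclude learning: both are done as fast as possible under rules, from a start signal on the stairs and with full extension and full return to sitting on the chair.

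**Silence is not absence.** The test descriptions cite a published recommended set and may be summaries, so staff may give practice anyway. A reader might also infer that the chair stand is a single first attempt, but the text gives one trial explicitly only for the stairs. Both points stand. Unwritten practice can, however, vary between subjects and visits.

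**Practice could backfire.** Exertion beforehand may matter more at baseline, when pain may be worse. This is a real but small risk, and the reason to keep practice minimal and add a rest.

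**Learning is one part of a larger limitation.** The study is openly an uncontrolled pilot, and practice does nothing for regression to the mean or placebo response. That is true, but learning is a part that can be reduced without adding an arm.

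**Conclusion.** This is a worthwhile low-cost improvement. It does not show that the primary analysis is wrong. As written, practice is described for one of three primary tests, and the design cannot separate learning on the other two from a treatment effect. If learning exists, it favours improvement.

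Its size is unknown. Assuming no drug effect and 60 evaluable subjects, the chance of a significant result per affected test runs from 1.7% with no learning to 45% at 0.3 SD of change two-sided, or 56% one-sided. The range is illustrative, and no value in it is more supported than another.

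It is tempting to express assumed learning as a share of the design effect, since "the effect size for this minimal detectable change is 0.392". The documents do not support that step. Section II.C derives 0.392 from a minimal detectable change and does not state its denominator, so it may not be in units of the SD of change.

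**What to change.** In II.E, add to the chair-stand section one or two untimed practice stands, and to the stair section one untimed ascent and descent. Follow each with a rest of fixed length before the scored trial. State the number of scored chair-stand trials. Do all of this identically at baseline and at weeks 6, 12 and 24.

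The cost is about two minutes per visit with existing staff and equipment, plus slight added exertion for people with painful knees, which minimal practice and the rest should limit. Sample size, endpoints and analysis do not change. The edit must come before baseline testing, because a baseline taken without practice cannot be corrected later.

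Practice will reduce learning without eliminating it, possibly on the walk test too. The report should therefore still describe the results as uncontrolled change from baseline.
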